4.6.1. Summary Table of Evaluations

Table 1Table of evaluations

Information Requested	Data Sourceª	Registration	Interim Prenatal Follow-up (end of 2 nd trimester)	Pregnancy Outcome	Infant Follow- up (4 & 12 months)	Targeted Follow-up
Maternal Information						
Maternal contact information, alternate contact information, HCP contact information	Participant and/or HCP	\checkmark	✓ b	✔ b	✓ b	
Maternal characteristics (age, ethnicity, etc)	Obstetric HCP	✓				
Maternal prenatal information (LMP, EDD, CEDD, prenatal imaging and aneuploidy screening/testing results & timing)	Obstetric HCP	\checkmark	✓ b	√ b		
Maternal disease severity (to include pre-conception assessment) ^c	SLE treatment Prescriber	\checkmark	✓ b	✔ b		
Obstetrical history	Obstetric HCP	\checkmark	√ b			🗸 d
Family history of birth defects	Obstetric HCP					🗸 d
Belimumab or other SLE treatment exposure information	SLE treatment Prescriber	\checkmark	√ b	✓ b	\checkmark	✔ b
Concurrent conditions, concomitant medications, pregnancy complications, alcohol, tobacco and recreational drug use during pregnancy	SLE treatment Prescriber and/or Obstetric HCP	~	✓ b	√ b		

BEL114256

Information Requested	Data Source ^a	Registration	Interim Prenatal Follow-up (end of 2 nd trimester)	Pregnancy Outcome	Infant Follow- up (4 & 12 months)	Targeted Follow-up
		Pregnancy Outcor	ne Information			
Pregnancy status	Obstetric HCP	\checkmark	\checkmark	√ b		
Outcome information (live birth, fetal loss, weight)	Obstetric HCP	√ e	√ e	\checkmark		
Birth defect noted & description	Obstetric HCP	√ e	√ e	\checkmark		
Contributing factors	Obstetric HCP	√ e	√ e	\checkmark		✔ d
		Infant Follow-up	Information		- · · ·	
Birth defect noted & description	Pediatric HCP			\checkmark	√f	✔ d
Contributing factors	Pediatric HCP			\checkmark	√f	🗸 d
Developmental milestones	Pediatric HCP				√f	
History of serious and/or clinically significant infections, fevers of unknown origin, treatment, & outcomes	Obstetric and/or Pediatric HCP			√f	√f	√ d
Breastfeeding status	Obstetric and/or Pediatric HCP			✓	√f	

a. Under ideal circumstances, the registry will collect data from the data source noted. Should there be extenuating circumstances that preclude data collection from the identified source; the registry may seek the data from a secondary source. Every effort will be made to verify patient reported data.

b. Obtain updated information since the previous contact.

c. Includes maternal disease severity pre-conception and at registration. If a registry participant does not have SLE, SLE specific assessments will not be required.

d. Collect information not previously obtained, to facilitate characterization of the fetal loss, birth defects or serious and/or clinically significant infections or fevers of unknown origin in the infant(s).

e. Obtain this information if outcome has occurred.

f. Collect only for live birth outcomes.

4.6.2. Registration Process

Registry enrollment will be voluntary and may be initiated by pregnant women or by their HCPs, who are acting as data reporters to the registry. After informed consent is obtained from eligible women, the participant and/or her HCPs will complete the *Registration Form* and the initial HCP data collection forms and submit them to the registry. The registry will provide a variety of conventional means for reporters to communicate with and submit data to the registry, including telephone, facsimile, postal mail, and email. The registry will provide a professional contact center in the US and Europe for communication with and collection of data from participants and their HCPs. The registry will also maintain a website that will provide information about the registry to facilitate participant registration and will also provide tools (e.g., down loadable CRF pages) that will facilitate the collection of accurate data.

The following information will be collected at registration.

Reporter Information

- Contact information for the participant as well as two alternate contacts outside the home to include name, address, phone number, and email address. This information will be verified and updated, as needed, at subsequent contacts with the participant.
- HCP reporter contact information

Maternal Information

- Maternal demographics
- Selected maternal medical history
- Previous registry participation
- Previous belimumab clinical trial participation
- Last menstrual period (LMP)
- Estimated date of delivery (EDD) determined from LMP
- Corrected estimated date of delivery (CEDD) (e.g., by ultrasound) if available
- Height
- Pre-pregnancy weight

Maternal Obstetrical History

- Number of previous pregnancies
- Outcome of previous pregnancies: live births, term births, preterm births, stillbirths, neonatal deaths, spontaneous miscarriages, elective terminations, ectopic pregnancies, and molar pregnancies
- History of offspring with birth defects
- Selected maternal conditions in previous pregnancies

• Prenatal imaging and aneuploidy screening/testing performed and findings including the identification of birth defects

Maternal SLE Disease Severity and Health Conditions within the 6 Months Prior to Conception and at Registration

- Baseline confirmation of SLE diagnosis by ACR criteria or clinical diagnosis
- Assessment for accrual of irreversible organ system damage by SDI
- Measurement of SLE disease activity by PGA If available:
 - Autoantibody testing results (anti-ds DNA, anti-cardiolipin antibodies, lupus anticoagulant, anti-Ro, anti-La)
 - Complement levels (C3/C4)
- Baseline assessment of proteinuria, serum and urine creatinine (urine protein/creatinine ratio preferred), (see Glossary)
- Other maternal conditions, e.g., thrombocytopenia and hypertension (see Glossary)
- Concomitant medications

Maternal Belimumab or other SLE treatment Exposure and Other Exposures (within 4 Months Prior to Conception and/or During Pregnancy)

• Belimumab or other SLE treatment course with dates of treatment. Dose and route of administration will be captured for belimumab exposed participants only. Tobacco, alcohol, and recreational drug use

4.6.3. Pregnancy Follow-up

Around the end of the second trimester and after pregnancy outcome, the *Obstetrical Follow-up Form, Obstetrical Pregnancy Outcome Form* (respectively) and *Pediatric Outcome Form* will be requested from the HCP. *SLE treatment Prescriber* data collection forms will also be requested from the HCP at these time points.

Information Collected at Interim Pregnancy Follow-up and Pregnancy Outcome

4.6.3.1. Follow-up at End of Second Trimester (~ 26 Weeks' Gestation)

Pregnancy Status

- Updates to EDD
- Subsequent prenatal imaging and aneuploidy screening/testing performed and findings including the identification of birth defects
- Pregnancy complications, if present
 - Pre-eclampsia/eclampsia (See Glossary)
 - Hypertension (See Glossary)

- Diabetes mellitus: pre-gestational/gestational (See Glossary)
- Details of pregnancy outcome as described below if pregnancy is not ongoing

Maternal SLE Disease Severity and Health Conditions

- Measurement of SLE disease activity by PGA If available:
 - Autoantibody testing results (anti-ds DNA, anti-cardiolipin antibodies, lupus anticoagulant, anti-Ro, anti-La)
 - Complement levels (C3/C4)
- Updated assessment of proteinuria, serum and urine creatinine
- Concurrent medical conditions (update on changes during pregnancy)
- Concomitant medications

Maternal Belimumab or other SLE treatment Exposure and Other Exposures

- Belimumab or other SLE treatment course with dates of treatment. Dose and route of administration will be captured for belimumab exposed participants only.
- Tobacco, alcohol, and recreational drug use

4.6.3.2. Information Collected at Pregnancy Outcome

Maternal SLE Disease Severity and Health Conditions

- Measurement of SLE disease activity by PGA If available:
 - Autoantibody testing results (anti-ds DNA, anti-cardiolipin antibodies, lupus anticoagulant, anti-Ro, anti-La)
 - Complement levels (C3/C4)
- Updated assessment of proteinuria, serum and urine creatinine
- Concurrent medical conditions (update on changes during pregnancy)
- Concomitant medications

Maternal Belimumab or other SLE treatment Exposure and Other Exposures

- Belimumab or SLE treatment course with dates of treatment. Dose and route of administration will be collected for belimumab exposed participants only.
- Tobacco, alcohol, and recreational drug use

Pregnancy outcome

- Date of pregnancy outcome
- Pregnancy type (singleton, twin, triplet, other)

- Subsequent prenatal imaging and aneuploidy screening/testing performed and findings including the identification of birth defects
- Pregnancy outcome (e.g., live birth, stillbirth, neonatal death, spontaneous miscarriage, elective termination, ectopic pregnancy, molar pregnancy)

Fetal Outcome

- Fetal/infant characteristics (e.g., gender, birth weight, length, head circumference)
- Birth defect(s) and assessment of potential contributing factors
- For a fetal loss (spontaneous miscarriage, stillbirth, ectopic pregnancy, molar pregnancy), factors that may have had an impact on the fetal loss and attribution
- Serious and/or clinically significant infections in the infant
- Breastfeeding status (see Glossary)

4.6.4. Infant Follow-Up

Pediatric Follow-up forms will be requested from the pediatric HCP for live-born infants at approximately 4 and 12 months of age:

- Date of assessment
- Weight, length and head circumference of the infant at birth if not provided at pregnancy outcome (at 4 month assessment)
- Infant date of birth
- Current weight
- Developmental milestones
- Birth defects identified
- History of serious and/or clinically significant infections and/or fevers of unknown origin since last contact, causative microorganisms if available, treatment, and outcomes
- Breastfeeding status
- Mother's belimumab or other SLE treatment exposure post-partum, if dosed while breastfeeding

4.6.5. Targeted Follow-up Process

The Targeted Follow-up process will gather additional information, if required to assist data interpretation, on events and outcomes of interest including adverse maternal outcomes, birth defects, other adverse pregnancy outcomes, serious and/or clinically significant infections in infants, infant growth and developmental milestones. This additional information may include:

• Details of the specific outcome (e.g., birth defects, other adverse pregnancy outcomes, serious and/or clinically significant infections in infants, infant growth

and developmental milestones) may be requested from the reporting HCP on the *Targeted Follow-up Form*

- Etiology of the specific outcome of interest
- Outcome attribution
- Lot number/s and expiry date/s of belimumab used to treat registry participants

4.6.6. Attempts to Obtain the Follow-Up Information

When follow-up is due for a registry participant, the HCP will be contacted and asked to provide follow-up information. Three subsequent attempts, as necessary, will be made approximately every 2 weeks through various modes of communication. If there is still no response from the HCP, a final communication will be sent indicating the case is lost to follow-up. If this communication prompts a response from the HCP, or from the participant or the requested data are later received at any point before the registry closes, the case will be re-opened and will no longer be considered lost to follow up. Once reopened, any data from assessments that had not been entered at the time the participant was lost to follow up (see Section 4.6.8.3) will be collected. If at any point in the follow-up process the reporter indicates that the participant is lost to follow-up, no further attempts will be made.

4.6.7. Follow-Up Process for Clarification of Information

If there are discrepancies in the data, the appropriate reporter(s) will be contacted for clarification. Three subsequent attempts, as necessary, will be made every 2 weeks. If no further information is obtained on an otherwise evaluable registry report (see Section 4.6.8.4), the discrepant information in the data fields may be left blank, identified as "unspecified." On a case-by-case basis, qualified registry staff or the principal investigator may make a determination on discrepant information (e.g., determination of partially illegible word or illogical year).

4.6.8. Registry Case Management and Disposition

4.6.8.1. Prospective Registry Reports

The registry will encourage prospective registration, which is defined as those exposures registered before the end of the pregnancy (i.e., live birth, fetal loss, etc). Two definitions for prospective reports of pregnancy will be used in this registry, traditional prospective and pure prospective [Holmes, 2008; Tomson, 2004]. Traditional prospective reports of pregnancy will include all women who enroll in the registry before the end of pregnancy (live birth, fetal loss, etc), regardless of known normal or abnormal prenatal test results. Pure prospective reports of pregnancy are a subset of traditional prospective reports and include those where (a) the enrollee did not know at the time of enrollment whether the fetus had a malformation, and (b) no prenatal testing was completed prior to enrollment. Reports of pregnancy defined as pure prospective will be included in the primary study population. Section 6 addresses the rationale, potential bias, and analytic techniques that may be employed to attempt to control for any known bias that may be introduced by this practice.

Prospective infant follow-up beyond the first year of life will not be routinely solicited by the registry but follow-up may be extended on a case-by-case basis if deemed medically necessary. In addition, while the study remains active, reports of birth defects that were identified in children after the 1st year of life and by 6 years of age will be entered into the database and reported in registry reports. This age criterion is consistent with CDC MACDP practice (see CDC MACDP Case Definition Criteria, 2015). Prospective reports of birth defects in infants beyond the first year of life and by 6 years of age will not be included in the primary study population, but will be described in the text of the registry final report. Prospective reports of infant infections beyond the first year of life will be forwarded to the sponsor for pharmacovigilance purposes only.

4.6.8.2. Retrospective Reports

Retrospective reports of pregnancy are those in which the pregnancy ended (live birth, fetal loss, etc) before enrollment or at the time of first contact with the registry. All retrospective cases reported to the registry will have data collected and entered into the database using the same procedures as prospective cases (traditional or pure); however, retrospective data will be summarized separately. Reports of pregnancy in which the pregnancy outcome or anticipated outcome is already known before enrollment can be biased toward the reporting of more unusual or severe cases compared to women whose pregnancy outcome is not yet known at the time of enrollment into the pregnancy registry. A woman or her HCP is more likely to notify the registry if a negative outcome is already known. Conversely, a woman or her HCP is less likely to notify the registry retrospectively if the pregnancy outcome was normal [Honein, 1999]. This potential enrollment bias could occur even for cases where the exposure information was obtained and documented in the medical record before the pregnancy outcome was known. Therefore, retrospective cases and traditional prospective cases will not be included in the primary study population, but will be summarized separately in interim and final reports to aid in detection of potential early signals. The frequency of birth defects in infants after the 1st year of life and by 6 years of age will be described in the text of the registry final report, stratified by traditional prospective, pure prospective and retrospective reports of pregnancy.

4.6.8.3. Lost to Follow-Up

For a prospective report or pregnancy where follow-up information on the pregnancy outcome, from a HCP, is never obtained, unavailable, and/or where the indication of a birth defect is designated as unknown, the pregnancy will be considered lost to follow-up. Cases lost to follow-up prior to pregnancy outcome will be tallied in the registry reports but not included in the primary study population. For infants, if pediatric follow-up information, from a HCP, is never obtained, unavailable, and/or where infant status is designated as unknown, the infant will be considered lost to follow-up. Any cases with infant outcome will be analyzed according to the length of infant follow up.

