4.6.8.4. Evaluable Registry Reports

An evaluable registry report is a case with data submitted or confirmed by a HCP that meets the minimum criteria for a registry report, as described in Section 4.1, and for which the pregnancy outcome is known. Pure prospective reported evaluable cases will

be included in the primary study population section of the registry report. Evaluable belimumab exposed traditional prospective and retrospective cases as well as unexposed cases will be summarized separately in the interim and final reports. Participant-reported data without HCP confirmation will also be summarized separately in the final report.

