4.8.2. Belimumab Analysis Population

The primary study population for which analyses will be presented includes pure prospective evaluable cases in participants having SLE considered exposed to commercially supplied belimumab (Section 4.4) that are not lost to follow-up (i.e., cases with appropriate outcome information that meet the minimum criteria for evaluation as specified in Section 4.1).

While the primary study population is pure prospective reported pregnancies, which can be used to ascertain actual population rates of events, the registry will complement its analyses by comprehensive review of other sources of information about pregnancy outcomes, including traditional prospective and retrospective reports.

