4.8.2.1. Exclusions for Analysis Purposes

Invalid cases (Section 4.6.8.5), pregnancies deemed lost to follow-up, retrospective cases, cases where participants do not have SLE, and SLE patients not exposed to belimumab will be excluded from the primary belimumab study population.

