As reporting of pregnancies will be totally voluntary, it is possible that even in pure prospective reported cases, potential bias could exist. For example, high-risk pregnancies or low-risk pregnancies may be more likely to be reported.

Those pregnancies that have reached EDD, but for which pregnancy outcome information was unobtainable after multiple attempts, will be considered lost to follow-up. It is possible that outcomes among pregnancies lost to follow-up could differ from those with documented outcomes. Because of differences in follow-up procedures across countries and individual reporting patterns, it is currently not possible to assess with any certainty what impact the potential biases the losses to follow-up may have on the analysis. However, efforts to compare some of the characteristics of each cohort may be conducted in an attempt to address this potential source of bias.

Fetal losses for which no birth defects have been reported may introduce misclassification bias. The percentage of these pregnancies consisting of potentially normal outcomes or birth defects is unknown. The data collection form will attempt to obtain information on birth defects detected at the time of the outcome. However, the reporting physician may not know the condition of the miscarried fetus.

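### Unknown birth-defect status alone makes a pregnancy lost to follow-up; this contradicts the evaluability rule and, if applied literally, can bias the miscarriage proportion downward

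*Protocol*

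**What the plan says.** Section 4.6.8.3 gives two routes to being lost to follow-up: no outcome information from an HCP, "and/or where the indication of a birth defect is designated as unknown, the pregnancy will be considered lost to follow-up". Either route is enough by itself.

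Section 4.8.2 builds the primary population from exposed, pure prospective, evaluable SLE cases "that are not lost to follow-up (i.e., cases with appropriate outcome information". Section 4.8.2.1 opens its list of exclusions with "Invalid cases (Section 4.6.8.5), pregnancies deemed lost to follow-up, retrospective cases" and does not limit the second item to pregnancies lost before their outcome.

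Three places point the other way:

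- Section 4.6.8.4 counts an HCP-confirmed case meeting the minimum criteria as evaluable when it is one "for which the pregnancy outcome is known", and places evaluable pure prospective cases in the primary population. Defect status is not a condition.
- The next sentence of Section 4.6.8.3 reads: "Cases lost to follow-up prior to pregnancy outcome will be tallied in the registry reports but not included in the primary study population". It is silent on cases lost only through the defect route.
- Section 6 describes loss to follow-up purely by outcome information that could not be obtained.

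Section 6 also accepts that "the reporting physician may not know the condition of the miscarried fetus". Spontaneous miscarriage and stillbirth are named secondary endpoints (Section 2.2). No section exempts fetal losses from the defect route or gives these endpoints their own population.

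**The concern.** Take a miscarriage confirmed by the obstetric HCP in which the fetus was not examined. Section 4.6.8.4 includes it in the primary population; Section 4.6.8.3 read with 4.8.2.1 excludes it. Two programmers could follow the protocol faithfully and report different miscarriage proportions.

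If the exclusion is followed, membership of the analysis set depends partly on the outcome being estimated. Section 4.3.2 counts defects in fetal losses of any gestational age, so the defect question arises for every miscarriage, where it is hardest to answer. A live-born infant has defect reporting at outcome and again at 4 and 12 months (Table 1).

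Fetal loss matters here. Section 1.1 cites 15-25% in the literature and 13 losses in 34 belimumab-exposed trial pregnancies with known outcome, elective terminations excluded. Nothing else in the protocol repairs such a selection. The traditional prospective analysis uses the same loss definition, which covers any prospective report. The baseline comparison of lost and evaluable cases in Section 4.8.4.4 describes the excluded cases but does not restore them.

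**Working it through.** **The plan's own figures.** The protocol gives no figure on this point. Its live-birth estimates in Section 5 reproduce (500 × 0.95 × 0.80 = 380; 500 × 0.83 × 0.75 = 311.25, stated as 311) and are not in dispute.

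**How each rule treats one case** (HCP-confirmed miscarriage, defect status unknown):

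| Place | Status | In primary population? |
|---|---|---|
| 4.6.8.3, first sentence | lost to follow-up | decided by 4.8.2 and 4.8.2.1 |
| 4.8.2.1 | lost pregnancies excluded | no |
| 4.8.2 | must not be lost; its gloss asks for appropriate outcome information | no, or yes if the gloss governs |
| 4.6.8.4 | evaluable | yes |
| 4.6.8.3, second sentence | not lost before the outcome | not named as excluded |
| 6 | not lost | yes, by implication |

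**Direction for miscarriage.** Let M be the true miscarriage proportion among known outcomes, u the share of miscarriages with unknown defect status, and v that share among all other outcomes. Under the literal rule:

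reported = M(1 − u) / [M(1 − u) + (1 − M)(1 − v)]

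This is below M when u > v, equal to M when u = v, and above M when u < v.

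**Size, as illustration only.** The same formula is applied with fetal losses pooled against live births. L is the true loss, spanning the 15-25% in Section 1.1. The shares u and v are assumptions; the documents give neither.

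| L | u = 25%, v = 0 | u = 50%, v = 0 | u = 50%, v = 5% |
|---|---|---|---|
| 15% | 11.7% | 8.1% | 8.5% |
| 20% | 15.8% | 11.1% | 11.6% |
| 25% | 20.0% | 14.3% | 14.9% |

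For L = 20%, v = 0: at u = 25%, 0.20 × 0.75 / (0.15 + 0.80) = 0.15/0.95 = 15.8%; at u = 50%, 0.10/0.90 = 11.1%.

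**Stillbirth.** Assume 15 miscarriages and 3 stillbirths per 100 known outcomes.

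- If half the miscarriages and no stillbirths are dropped, 92.5 remain. Stillbirth is 3/92.5 = 3.2%, above the true 3%.
- If half of both are dropped, 91 remain. Stillbirth is 1.5/91 = 1.6%, below it.

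The sign depends on where unknown status falls.

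**Birth defects.** Sections 4.8.1 and 4.8.4.2 divide by live births and add to the numerator only fetal losses with a reported defect. A fetal loss of unknown status enters neither, so dropping it changes nothing.

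**The case against.** The strongest reply is that the protocol means an outcome-only rule and Section 4.6.8.3 is loosely worded. Besides the three places already set out, the gloss in Section 4.8.2 speaks of outcome information. Section 6 also warns that fetal losses without a reported defect may be misclassified, which makes sense only if they stay in the data. This stands as evidence of intent. It does not settle the text: an outcome-only reading leaves the defect route without effect, and Section 4.8.2.1 still excludes every pregnancy deemed lost.

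The size is also fairly challenged. Only cases designated unknown trigger the rule, so the unknown share depends on whether a loss with nothing noted is recorded as no defect or as unknown, and the documents do not show this. The table pools fetal losses, whereas Section 4.8.4.1 estimates miscarriage separately among pregnancies enrolled before week 20, stratified by gestational age at enrollment. Elective terminations may have unknown status too, which would raise v and offset part of the effect. These points stand, so the figures are scenarios.

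The affected endpoints are secondary and descriptive, and Section 4.8.3.2 already cautions about external comparisons. That limits the consequence but does not remove the contradiction.

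**Conclusion.** The contradiction is certain on the text, and the exclusion as written would remove documented miscarriages from a named secondary endpoint. The downward bias is conditional on the literal rule being applied and on unknown defect status being commoner in miscarriages than in other outcomes. Section 6 makes the second condition plausible without quantifying it.

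A reader might infer more than the documents support:

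- *That fetal loss will be understated.* The protocol also contains the opposite rule, and the unknown share is not given.
- *That Section 6 says defect status is often unknown after miscarriage and nearly always known for live births.* It says only that the physician may not know, gives no frequency, and makes no such comparison with live births. The contrast is an inference from the reporting schedule.
- *That stillbirth is biased downward as well.* Section 6 refers to the miscarried fetus only, and the stillbirth proportion can rise.
- *That the primary endpoint is compromised.* Dropping fetal losses of unknown status leaves birth-defect prevalence unchanged.

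**What to change.** Define loss to follow-up by endpoint:

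- **Pregnancy-outcome endpoints:** lost only if no HCP-confirmed pregnancy outcome was obtained. A pregnancy with a known outcome and unknown defect status stays in every pregnancy-outcome analysis.
- **Birth-defect endpoint:** the same pregnancy is non-evaluable for this endpoint only. Report how many there are.

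Align Sections 4.6.8.3, 4.6.8.4, 4.8.2, 4.8.2.1 and 6 with this wording, and carry it into the RAP before analysis. The cost is a short text change and one derived flag. Table 1 already collects pregnancy outcome and birth-defect information, so no new data are needed.
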